#### **7.5.2. Sensitivity Analyses of the Primary Efficacy Results**

Several sensitivity analyses are planned:

1. Analysis restricted to time eligible for dPEP (i.e., no active pregnancy). Time in both arms will be censored at the study visit when a participant was determined to be not pregnant (from visit with first positive pregnancy test until exit without re-entry into risk set)
2. Time to first STI (from randomization) using Kaplan Meier and Cox PH regression. All women will be treated as at risk for all STIs at randomization. It is acknowledged that women diagnosed with an STI at a visit are treated until cure, and thus are not immediately at risk. However, women re-enter the risk set when cured, thus are at risk prior to the next quarterly visit.
3. Defining an STI as incident, in the case where the same STI was previously present, only if a negative test for the same pathogen is recorded before the positive result. The

primary outcome will be modified to exclude any repeat STI without a preceding negative result, and the statistical analysis for the primary analysis repeated.

4. Analysis counting all individual STIs diagnosed in a quarterly interval A Poisson model fitted using GEE methods to account for multiple events from each participant will be used to estimate the change in rate of infections between arms. If necessary to achieve a better more fit, a zero-inflated Poisson model may be used.

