### **Pregnancy, breastfeeding, and HIV seroconversion**

#### *Management of dPEP with contraceptives and pregnancy:*

Contraception will be offered on-site but will not be required for study participation. The effectiveness of contraceptives or dPEP will not change with concomitant use. Women will be counseled on current Kenyan guidelines, which do not recommend use of doxycycline in pregnant women and participants

will stop dPEP should pregnancy occur. Women, who are not using LARC, will be screened for possible pregnancy at each quarterly visit using the WHO pregnancy checklist and if needed a urine pregnancy test will be conducted. Women will be counseled on current Kenyan guidelines, which do not recommend use of doxycycline in pregnant women and participants will stop dPEP should pregnancy occur; women can resume dPEP when no longer pregnant or breastfeeding. Pregnancies will be followed to completion. Any babies born to participants during the trial period will be passively followed for 1 year following their birth. Participants who deliver a baby during the trial will be asked to return for scheduled, quarterly study visits for a total of up to 12 months even though dPEP will be stopped if they are in the dPEP group. Additionally, they will be asked about the health of their baby at each study visit with continuation of questionnaire on health of their infant for first 12 months of infant's life. Breastfeeding will be an exclusion criterion for the trial, to limit exposure prior to demonstration of effectiveness; doxycycline is generally felt to be safe at standard doses in lactating women, although no formal declaration of safety exists for this population. Doxycycline is well-tolerated and recent data emphasize a strong safety profile when used by women, including in early pregnancy. Early data on safety of tetracycline found potential adverse effects when used in late pregnancy (specifically, bone and tooth effects), and cautions were extended to the entire tetracycline class, including doxycycline, despite lack of drug-specific data. Expert opinion is now calling for reconsideration of doxycycline use in pregnancy given significant differences between doxycycline and tetracycline and lack of evidence showing adverse events with doxycycline exposure in pregnant women.

*Management of PrEP with contraceptives and pregnancy:*

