## 9.0 CRITERIA FOR DISCONTINUATION

### Premature Study Treatment Discontinuation

- Requirement for prohibited concomitant medications or other contraindication to doxycycline
- Occurrence of an AE requiring discontinuation of doxycycline
- Request by participant to terminate study treatment
- Clinical reasons believed life threatening by the physician, even if not addressed in the toxicity section of the protocol
- Requirement for chronic tetracycline use (>14 days)
- Pregnancy
- Breastfeeding

Participants who stop dPEP should be continued on study, off dPEP with continued evaluations. The reason for doxycycline discontinuation should be recorded.

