### **Statistical analysis**

Comparison of STI incidence by arm will be conducted by estimating the relative risks of any STI over the 3, 6, 9 and 12 month visits using a modified Poisson model fitted using GEE methods to account for repeated observations from each participant, assuming an independent covariance structure, with study arm as the only covariate[1]. The test for significance will be a two-sided alpha = 0.05. 95% confidence intervals will be computed using robust standard errors.

The same analysis will be repeated for the individual STIs.

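### The pregnancy sensitivity analysis (SAP 7.5.2, item 1) has a reversed censoring trigger, and its bar on re-entry does not match its label of time eligible for dPEP

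*SAP*

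**What the plan says.** SAP 7.5.2 lists four sensitivity analyses of the primary efficacy result. Item 1 gives its purpose as "Analysis restricted to time eligible for dPEP (i.e., no active pregnancy"). The rule that applies it comes in two parts:

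- Main clause: "Time in both arms will be censored at the study visit when a participant was determined to be not pregnant".
- Parenthesis: "from visit with first positive pregnancy test until exit without re-entry into risk set".

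The protocol's section on pregnancy, breastfeeding and HIV seroconversion states that "participants will stop dPEP should pregnancy occur" and also that "women can resume dPEP when no longer pregnant or breastfeeding". Protocol 9.0 lists both pregnancy and breastfeeding as reasons for stopping study treatment, and adds: "Participants who stop dPEP should be continued on study, off dPEP with continued evaluations". Visits after a pregnancy are therefore planned, and the analysis must either use them or leave them out.

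The analysis being varied is the one in SAP 7.5.1, which works by "estimating the relative risks of any STI over the 3, 6, 9 and 12 month visits" in all randomized women.

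**The concern.** The two parts of the rule name opposite events as the trigger. No other section of the SAP or protocol says which one governs.

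The second problem remains once the trigger is corrected. Eligibility for dPEP can return under the protocol, but the parenthesis excludes a woman permanently after her first positive test. The label promises eligible time, and the rule delivers time before the first pregnancy. Those are different quantities, and a reader of the results would be told the wrong one.

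The timing makes the wording worth settling. The revision table in SAP Section 10 records that sensitivity analysis plans were added after the 2/3 interim review, and SAP Section 1 requires a final SAP before database lock. Text with two opposite triggers leaves the analyst to choose a reading at the end of the trial.

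**Working it through.** The documents state no figure for this analysis, so there is none to reproduce. The check applies each reading to the visit schedule and then sizes the loss.

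**Step 1: the main clause taken literally.** Pregnancy is an exclusion criterion (Protocol 4.0), and every woman is tested at the enrollment visit. Each participant is thus found not pregnant at the start, so censoring at that finding would leave nothing to analyse. The only workable literal reading is to censor at the first not-pregnant visit after a pregnancy.

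**Step 2: one woman.** She tests positive at month 3 and by month 6 is neither pregnant nor breastfeeding and has resumed dPEP.

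| Visit (interval ending there) | Stated purpose | Parenthesis | Main clause, workable literal reading |
|---|---|---|---|
| Month 3 | partly pregnant; arguable | out | kept |
| Month 6 | began pregnant; out | out | out |
| Month 9 | eligible; keep | out | out |
| Month 12 | eligible; keep | out | out |

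The main clause keeps the visit at which she was pregnant and drops both fully eligible intervals. The parenthesis handles the pregnancy but drops the same two intervals. (It is shown as excluding the month 3 result, although the wording does not settle that.)

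**Step 3: eligible intervals lost through no re-entry.** Inputs from the SAP: N = 446 (3.3.1) and four scheduled visits (7.5.1), so 446 × 4 = 1,784 intervals before dropout. Assumptions, because the documents give no figures: pregnancy incidence r of 0.05, 0.10 or 0.20 per woman-year, and 20% of pregnancies ending within a quarter of detection with no breastfeeding afterwards.

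The chance of a first positive test in a quarter is q = 1 − exp(−r/4). A first positive at month 3 costs two eligible intervals, at month 6 one, and later none:

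lost = 0.20 × [2 × 446q + 446(1 − q)q]

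- r = 0.05: 0.20 × (2 × 5.5 + 5.5) = 3.3 (0.2% of 1,784)
- r = 0.10: 0.20 × (2 × 11.0 + 10.7) = 6.6 (0.4%)
- r = 0.20: 0.20 × (2 × 21.8 + 20.7) = 12.8 (0.7%)

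The protocol's 550 women would scale the counts by 550/446 and leave the percentages unchanged.

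**Step 4: simulation as a cross-check.** It took 223 women per arm (892 visits, no dropout), the same pregnancy rates, and 15% to 30% of pregnancies ending 1 to 4 months after conception. The rest delivered at 9 months and then breastfed. The parenthesis removed about 25 to 100 visits per arm, of which about 2 to 14 were eligible. Over two arms that is about 4 to 28 of 1,784 (0.2% to 1.6%). This is higher than Step 3 because it classes a visit by the woman's status on the day, so month 6 in the table would count as eligible, and because its early-loss range extends to 30%. Programmed literally, the main clause lost the same eligible visits and retained about 20 to 84 pregnant visits per arm (2% to 9% of 892).

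**The case against.** The best defence is that this is one stray word. The purpose and the parenthesis agree, the parenthesis gives a start, an end and a re-entry rule, and a programmer could work from it alone. It is also fair that the protocol's statement on resuming dPEP is a permissive clinical provision and does not define a risk set. Permanent censoring at first pregnancy is a legitimate choice, and the per-protocol analysis in SAP 7.5.3 uses a similar convention by stopping at the first discontinuation. All of this stands. It reduces the first problem to a probable slip and the second to a mismatch between label and rule. Neither disappears: the slip is uncorrected, and the label still claims eligible time. Item 2 of the same list shows that re-entry was considered for treated STIs: "However, women re-enter the risk set when cured, thus are at risk prior to the next quarterly visit".

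A reader might infer more than the documents support:

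- *That the first-positive visit is wrongly discarded, costing 1.2% to 4.5% of intervals on drug.* A pregnancy first detected at a quarterly visit normally began during the preceding interval, so that interval is partly pregnant time and either treatment is defensible. The wording does not settle whether that visit's result is dropped. The percentages also count both arms, and standard-of-care women had no study drug.
- *That omitting breastfeeding is a separate error.* Breastfeeding women are excluded at entry, and breastfeeding after an on-study pregnancy is already censored while re-entry is barred. It matters only if re-entry is allowed.
- *That this is the only efficacy analysis tied to women who could take dPEP.* SAP 7.5.3 restricts dPEP-arm time by discontinuation, and SAP 8.5.2 compares use with non-use.
- *That the lost quarters carry the highest STI exposure.* Nothing in the documents shows this.

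**Conclusion.** The point holds as two defects of wording in one sensitivity analysis. The main clause has its trigger reversed. With that corrected, the bar on re-entry makes the analysis one of time before first on-study pregnancy, not of time eligible for dPEP.

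The size is small: about 3 to 13 of 1,784 intervals lost through no re-entry, on assumed pregnancy rates of 5 to 20 per 100 woman-years with 20% ending early. Counting by status on the visit day and allowing up to 30% early loss raises the upper end to about 28. The reversed trigger would do more damage if programmed as written, because pregnant visits would stay in.

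It would be wrong to read this as a breach of the protocol's clinical rule or as a threat to the main result. The primary analysis is intention-to-treat with no pregnancy censoring and is unaffected.

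**What to change.** Before database lock, in SAP 7.5.2 item 1:

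1. Change the trigger from *not pregnant* to *pregnant*, so that main clause and parenthesis agree.
2. Make label and rule match, in both arms, by one of two routes:
   - (a) keep the bar on re-entry and retitle the analysis *time before first on-study pregnancy*; or
   - (b) where pregnancy and breastfeeding status are recorded, allow re-entry at the first scheduled visit after an interval that began with the woman neither pregnant nor breastfeeding, and add breastfeeding to the definition of ineligible time.
3. State whether the STI result at the first-positive visit is included.

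Route (a) costs a few words. Route (b) needs some programming and depends on the data. The protocol's visit schedule makes follow-up urine pregnancy tests conditional on clinical indication, the pregnancy checklist applies to women not using long-acting contraception, and the schedule shows no breastfeeding item, so that status might have to be derived from the questions on infant health. SAP version 4.0 was prepared as data collection was ending, so check that these fields exist before choosing (b).

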### **7.5.3. Analyses of the Primary Efficacy Results while on study drug (Per protocol)**

For the per-protocol analysis, for each cohort the dPEP arm will be restricted to study time prior to the first discontinuation (> 2 weeks) of study drug documented on the study dPEP CRF. The evaluation of the impact of doxycycline on Any STI will use the same model as specified for the primary analysis, but also potentially adjusted for age, baseline STI, baseline and follow-up sexual risk (number of partners, nulliparous, contraceptive use, transactional sex).

### **7.6. Study drug use and time on study drug in the dPEP arm**

- Study drug dispensation (number of participants and number of pills) will be summarized for each study visit over time by cohort.
- Longitudinal exposure to doxycycline will be assessed using hair collection, with a semi-quantitative evaluation in 10% the control arm (doxycycline present vs. absent) and quantitative evaluation in the 100% of dPEP arm (doxycycline concentration value).
- Proportion of time on study drug in the dPEP arm, based on discontinuations documented on study CRFs will be tabulated for each quarter and overall by study arm within each cohort.
- Concomitant use of antibiotic use as documented in the antibiotic use log, will be summarized for the control and dPEP arms

### **7.7. Analysis of Tetracycline resistance**

#### **7.7.1. Analysis of TCN resistance in GC cases**

TCN resistance will be assessed in GC cases only. TCN resistant GC will be defined by the detection of plasmid-mediated *tetM* gene conferring high-level tetracycline resistance.

Descriptive statistics: Tabulations of resistance (No GC, GC: TNC resistance testing = missing, not resistant, resistant) will be reported at baseline, 3, 6, 9 and 12 month visits in GC cases in each arm.

Statistical analysis: Assessment of odds of resistance by arm will be assessed by estimating the odds of GC infection with resistance among cases detected after enrollment using logistic regression, adjusted for visit.

Sensitivity analysis: molecular chromosomal mutations may lead to expression of tetracycline resistance. Tabulations of number of expressed chromosomally-mediated tetracycline resistance determinants (*mtrR*, *rpsJ*, *porB*, and *pilQ*) will be reported at baseline, 3, 6, 9, and 12-

month visits in GC cases, among those with or without plasmid-mediated tetracycline resistance (i.e., detection of *tetM*), in each arm.

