**State-of-the-art assessment of antimicrobial resistance.** Over the past 14 years, [name] has worked extensively in the field of gonococcal antimicrobial resistance (AMR). [name] laboratory characterizes molecular mechanisms of AMR in *N. gonorrhoeae* isolates and is a core laboratory for CDC's national gonococcal AMR surveillance project, and he has identified isolates with unique AMR profiles. Preliminary results from frozen STI+ endocervical swab samples from Kenyan women in our Partners PrEP Study (i.e., \*not\* using dPEP) were tested for tetracycline resistance using the molecular methods: 50 with *N. gonorrhoeae* and 10 with *C. trachomatis*. Detection of tetracycline-resistance was high for *N. gonorrhoeae* (*tet*(M)=48/50, 96%), suggesting resistance may be at a ceiling in the community already, prior to dPEP use, but also that dPEP may not be effective against *N. gonorrhoeae*. No *C. trachomatis* organisms had resistance (*tet*(C)=0/10, 0%).

**Mathematical modeling and costing studies help to define optimal models for PrEP delivery.** Led by [name], we have used costing methods and mathematical modeling to address key questions related to how to best deliver PrEP. For serodiscordant couples, we found the cost of PrEP per infection averted is significantly offset by future savings in ART costs, especially time-limited PrEP – used prior to and early after ART initiation by an HIV infected partner, when risk is highest. These results were a key basis for designing our “PrEP as a bridge to ART” strategy in the Partners Demonstration Project. Second, we used methods for development of clinical prediction rules to derive a risk scoring tool for couples. Our work has been a model for risk scores for other populations – for example, the VOICE score for women at risk – and for programmatic prioritization of subpopulations for PrEP. Third, micro-costing, time and motion work, and mathematical modeling have helped define the annual cost of PrEP (~US\$100) for the Kenya Ministry of Health.

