#### *Testing for tetracycline resistance among *N. gonorrhoeae**

Molecular characterization of *N. gonorrhoeae* will include strain typing using the internationally frequently used *N. gonorrhoeae* multiantigen sequencing typing (NG-MAST) system, and detection of *tetR* including plasmid-mediated *tet(M)*; and chromosomally-mediated resistance determinants: *mtrR* (A39T, G45D, G45S, -35delA and -10insTT), *rpsJ* (V57M), *porB* (G120K, A121D/N), and *pilQ* (E666K) by PCR and sequencing. Well-characterized positive control strains and negative controls will be included in all PCR assays. The detection of the plasmid-encoded *tet(M)* gene and/or *tetR* genetic resistance determinants is indicative of phenotypic resistance to tetracycline, doxycycline, and minocycline. All samples with the same NG-MAST sequence types will be further differentiated by multilocus sequence typing. Whole genome sequencing will be conducted on endocervical swabs from patients with the same strain types and *tetR* genotypes and rigorous investigation of single nucleotide polymorphisms associated with novel resistance mechanisms will be performed.

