### Secondary outcomes:

- Safety: Safety assessment will be measured in both arms: serious adverse events (SAEs), related all AEs and discontinuations (in the dPEP arm only), and a standardized symptom assessment for doxycycline-specific side effects (e.g., nausea, pill esophagitis, photosensitivity, vaginal candidiasis).
- Acceptability: Longitudinal change in qualitative themes and associated barriers and facilitators
- Adherence: We will explore the self-reported measures and SMS data, defining adherence as the percentage of times that dPEP was taken following an episode of condomless intercourse. Stored vaginal swabs for Y chromosome testing can be available for later validation.
- Resistance: The detection of the plasmid-encoded *tet(M)* gene and/or *tetR* genetic resistance determinants is indicative of phenotypic resistance to tetracycline
- Cost: The incremental cost effectiveness ratio (ICER) per incident STI case averted and DALY averted

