Acceptability: Quantitative analysis will be completed using GEE to test associations between facilitators/barriers and randomization arm, dPEP adherence, and STI outcomes. Data will be analyzed to understand factors impacting acceptability of dPEP, including demographics, stigma, fertility desire, dPEP effect on sexual and preventative decision making. Qualitative analysis will take a longitudinal approach. Interview discussions will be recorded, transcribed, and translated into English. Transcripts will be reviewed separately by two investigators for completeness and initial theme generation. We routinely use rapid debriefing reports to obtain real-time information; formal coding and analysis will be performed with Atlas.ti, using inductive approach informed by theoretical framework of acceptability (TFA), a recently developed approach to acceptability research of medical interventions. The components of TFA are affective attitude, burden, ethicality, intervention coherence, opportunity costs, perceived effectiveness, and self-efficacy. Initial code generation of the transcript themes will capture experiences and context of dPEP use. Codes will be reviewed for consistency and inter-coder agreement with consensus code generation by themes. Following a similar process, transcripts from Months 6 and 12 will be coded with reference to the baseline codes to capture temporality of experiences and contexts within each participant. Codes generated from transcripts at Months 6 and 12 will be compared across participants to establish differences and similarities across the sample. The code will reflect the longitudinal data and emergence of new codes. Descriptive thematic analyses will be done at baseline and over time.

Resistance: The impact of dPEP on *C. trachomatis* and *N. gonorrhoeae* resistance will be measured by comparing the overall rates of doxycycline-resistant events occurring in the dPEP arm to rates in the

control arm, at baseline and separately during follow-up adjusted for medical factors that confound the dPEP-resistance risk relationship.

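### SAP 7.7.1 narrows the protocol's gonococcal resistance outcome to plasmid tetM alone; chromosomal determinants get a by-arm table but no effect estimate, and a null tetM result may say little

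*SAP*

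**What the plan says.** **Protocol.** The laboratory section on tetracycline resistance in N. gonorrhoeae lists plasmid tet(M) "and chromosomally-mediated resistance determinants" (mtrR, rpsJ, porB and pilQ). It then says that finding tet(M) and/or tetR "genetic resistance determinants is indicative of phenotypic resistance to tetracycline, doxycycline, and minocycline". Section 10.0 repeats this as the resistance outcome: tet(M) and/or tetR "genetic resistance determinants is indicative of phenotypic resistance to tetracycline". The planned analysis, also in section 10.0, is "comparing the overall rates of doxycycline-resistant events occurring in the dPEP arm to rates in the" control arm, at baseline and separately during follow-up.

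**SAP.** Section 2.2.5 names the endpoint broadly, as molecular markers of resistance for GC. Section 7.7.1 is narrower: "TCN resistant GC will be defined by the detection of plasmid-mediated" tetM. The by-arm model is a logistic regression adjusted for visit on that outcome: "Assessment of odds of resistance by arm will be assessed by estimating the odds of GC infection with resistance among cases detected after enrollment". The same section accepts that chromosomal mutations can produce resistance. Its provision for them, headed as a sensitivity analysis, is "Tabulations of number of expressed chromosomally-mediated tetracycline resistance determinants" at baseline and months 3, 6, 9 and 12, by tetM status and arm. No model, interval or test is attached. The revision table in SAP section 10 does not mention the definition.

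**Background level.** Protocol section 1.0 reports tet(M) in 48 of 50 GC samples from Kenyan women not using dPEP, "suggesting resistance may be at a ceiling in the community already". It also cites 73% to 97% for plasmid-mediated resistance in Africa.

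**The concern.** The same isolate can be classed two ways. GC with no tetM but with chromosomal determinants is resistant under the protocol. Under the SAP it is not resistant, both in the main table and in the only arm contrast that yields an estimate.

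The marker left in the model may also have little room to rise. If nearly all circulating GC already carries tetM, an odds ratio for tetM cannot show much selection even if selection occurs, and a reader may take a null result as reassurance.

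Resistance is a primary objective in protocol section 3.0, although its outcome is listed as secondary in section 10.0 and SAP 2.1.2 makes it a secondary objective. The protocol's DSMB section makes a significant change in doxycycline-resistant STIs a ground for recommending a stop. SAP 4.1 asks that any efficacy stop be balanced against the need for evidence on acquired resistance. Those judgements need one stated definition.

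**Working it through.** **1. The two definitions side by side**

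| Isolate | Protocol | SAP 7.7.1 |
|---|---|---|
| tetM present | resistant | resistant |
| tetM absent, chromosomal determinant present | resistant | not resistant |
| neither | not resistant | not resistant |

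Only the middle row differs. The protocol's and/or wording makes sense only if tetR is wider than tet(M), and its list of chromosomal determinants supports that reading.

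**2. The protocol's own figure.** 48/50 = 96.0%, as stated. The exact (Clopper-Pearson) 95% CI is 86.3% to 99.5%, so the tetM-negative share is 4.0% (0.5% to 13.7%).

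**3. Expected GC cases per arm.** Inputs: 223 women per arm and 10% loss (SAP 3.3.1); GC incidence of 11% to 20% per year (protocol Table 3). Assumptions: one year of follow-up, one case per infected woman, no dPEP effect on GC.
- Low: 223 × 0.90 × 0.11 = 22.1
- High, no loss: 223 × 0.20 = 44.6

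This gives about 22 to 45 cases per arm. With the protocol's 275 per arm, the high end is 275 × 0.20 = 55.

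**4. Power of the tetM contrast.** The comparison takes the most extreme case, in which every dPEP-arm isolate is tetM positive. A two-sided Fisher test at 0.05, enumerated exactly, stands in for the planned logistic model. With no tetM-negative isolate in the dPEP arm, the test rejects only if the control arm has at least 5 (n = 22) or at least 6 (n = 28 to 55). At 4% negative the control arm is expected to have 22 × 0.04 = 0.9 to 45 × 0.04 = 1.8.

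| Cases per arm | from 96% | from 86.3% | from 73% |
|---|---|---|---|
| 22 | 0.15% | 17% | 75% |
| 28 | 0.07% | 18% | 81% |
| 40 | 0.5% | 47% | 98% |
| 45 | 0.9% | 59% | 99% |
| 55 | 2.2% | 78% | 99.9% |

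The 86.3% column is the lower confidence limit from step 2; the 73% column is the low end of the cited African range.

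**5. How many isolates the definition could move.** At most, all tetM-negative isolates in both arms:
- tetM at 96%: 2 × 22 × 0.04 = 1.8 to 2 × 45 × 0.04 = 3.6
- tetM at 73%: 2 × 22 × 0.27 = 11.9 to 2 × 45 × 0.27 = 24.3

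Let q be the share of tetM-negative isolates with a chromosomal determinant. Prevalence under the protocol's definition is tetM + (1 − tetM) × q. The documents do not give q. Over q = 0 to 1, the result is 96% to 100% if tetM is 96%, and 73% to 100% if tetM is 73%.

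**The case against.** Four points can be made for the SAP.

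- **Chromosomal determinants are not ignored.** They are tabulated by visit, tetM status and arm. A reader might infer that they go uncompared between arms. The text does not support that; what is missing is an effect estimate with an interval.
- **The ceiling is not established.** The protocol says only that resistance may be at a ceiling, from 50 samples, and also cites 73% to 97%. A reader might infer that the tetM model would show no difference almost whatever dPEP does. The power table supports this only near 96%; at 73% a rise to 100% would usually be detected. Nor can one say that the chromosomal determinants are the only part of the genotype still able to change. No document gives their baseline prevalence, so they may be near a ceiling too.
- **The protocol's definition does not cure the ceiling.** It can only raise prevalence, and at 96% tetM it moves at most about 2 to 4 isolates. The definitional conflict and the ceiling are separate problems: the first is largest when tetM is low, the second when tetM is high.
- **A descriptive table is defensible for a sparse marker.** With no baseline prevalence, the precision of a modelled comparison cannot be worked out in advance.

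All four stand as limits on the claim. None explains why the modelled outcome is narrower than the protocol's. A sparse comparison is also a reason to show the interval, since a bare table leaves readers to judge the imprecision themselves.

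**Conclusion.** The definitions conflict on the face of the documents, and the SAP's only stated ground is that tetM confers high-level resistance. The modelled comparison therefore does not address the protocol's outcome, and chromosomal determinants have a descriptive by-arm table only.

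The size depends on tetM prevalence in this population. Near 96% the tetM contrast is almost uninformative (0.1% to 0.9% power for a rise to 100%), and few isolates are classed differently. Near 73% the contrast has useful power (75% to 99%), but as many as 12 to 24 isolates could be classed differently. This rests on 22 to 45 cases per arm, no dPEP effect on GC, and Fisher's test as an approximation to the planned model. Fewer GC cases in the dPEP arm would leave less information.

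This is worth correcting because the data will exist and the wording is easily fixed. It does not show that the resistance analysis must fail.

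**What to change.** In SAP 7.7.1:

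1. Label the tetM outcome as high-level, plasmid-mediated resistance, and report the protocol's tet(M) and/or tetR outcome beside it, by arm. If the narrowing is deliberate, state why.
2. Add a secondary by-arm estimate with 95% CI for chromosomal determinants after enrollment, as the number per isolate or any versus none, with baseline values shown. Allow for clustering by woman; SAP 7.7.2 already provides for GEE with repeat CT infections, and 7.7.1 has no such provision.
3. State that tetM may be near its ceiling, and that a null tetM result there is not evidence of no selection.

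The protocol already plans the laboratory work, so the cost is SAP wording and one further secondary comparison. That comparison will be imprecise at these case numbers and should be labelled so. Using the protocol's definition resolves the conflict but does not by itself make the arm contrast more informative.
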